1. arresting of the lesions – restorative treatment may no longer be necessary, but, in case the child are waiting for treatment under GA, they will not lose their place, and restorative treatment will be offered if parents will still want it because of esthetic reasons;
2. staining of the teeth – when lesion is arrested, damaged dental enamel and dentine often change colour, become darker, and the treatment methods can facilitate that (especially SDF), and therefore the teeth can become unattractive;
3. unpleasant taste during the procedure.

[figure not shown]

Fig 2. Flow chart of the clinical trial.

If the parents agree to the study, they will be assigned an appointment with one of two calibrated examiners, who will again explain the study and in whose presence, they will sign the informed consent form. If the parents for some reason decide not to participate, they can withdraw without any negative consequences. The calibrated specialist will perform a damage progression and activity register (ICDAS, Nyvad criteria) and draw lots with a closed envelope, of which group the patient will be included in (with a color code).

The patient, with information about their group's color goes to another office, where one of four trained dentists and assistants will be working (Intervention staff - IS). They will be informed about the medication to be used in each of the groups. The corresponding treatment method will be applied, and the child will be asked to describe their feelings during the procedure by using visual

analogue scale (VAS), the next visit will be set according to the group's corresponding protocol. On all future treatment appointments, the patient will only see the dentists and assistants of IS.

After the last application foreseen in the protocol, the patient will be assigned a control appointment, which will be 12 months after the first examination. During the control appointment one of the calibrated examiners will perform a documentation of stage and activity of carious lesions, not knowing which treatment had been applied. The questionnaires for the parents and children about their satisfaction with the appearance of their teeth will be applied.

Interventions

Patients who agree to participate in the study, will be randomly placed into one of six groups:

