MS2.2 Workshop with [name] and [name] in the University of Michigan.

MS2.3 Preparation of informed consent.

MS2.4 Preparation of Patient satisfaction assessment form.

MS2.5 Preparation of Emergency treatment form.

MS2.6 Preparation of initial examination form.

MS2.7 Preparation of follow-up examination form.

MS2.8 Preparation of the report on the adaptation of ICDAS and Nyvad systems used within the context of the specific aims of the study (related to WP3, task 3.3).

3. **WP3** Training and calibration. **The objective of WP3** is to train dentists, assistants (dental hygienist students) and postgraduate students of RSU Institute of Stomatology to perform different tasks during the study and to calibrate two examiners to ensure the quality of the data:
 1. Training of staff at the Department of Paediatric Dentistry of Institute of Stomatology – for their role in patient recruitment, dissemination of information and activities in case of emergency treatment required for children in the study (general staff (GS) training).
 2. Training of four dentists (postgraduate students in paediatric dentistry) – and two assistants (dental hygienist students) for treatment methods to be applied to all groups of the study (“Intervention staff” (IF)).
 3. Training and calibration of two examiners on detecting the stage and activity of carious lesions – postdoctoral researcher and another dentist from the Department of Paediatric Dentistry.

Deliverables of WP3

D3.1 Report on GS training.

D3.2 Guidelines and registration form to enrol patients in the study.

D3.3 Guidelines about performing and documenting emergency treatment for children of the clinical trial.

D3.4 Report on IS training.

D3.5 Report of examiners calibration.

Milestones of WP3

MS3.1 GS training session.

MS3.2 IS training session.

MS3.3 Examiner calibration session.

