4. **WP4** Clinical trial. **The objective of WP4** is to perform the clinical trial according to an established protocol and the highest ethical standards with the primary aim of finding out which high-concentration fluoride application method and which application protocol more effectively protects pre-school children from complications arising from early childhood dental caries. Secondary objectives are to evaluate at which stage of development (cariou lesions) the methods are the most effective; which fluoride application method and protocol is more effective in arresting non-cavitated and cavitated cariou lesions in preschool children; how satisfied are parents and patients with SDF and Tiefenfluorid application procedures and side-effects (staining) and what are the costs and cost-effectiveness of each method and application protocol.
 1. Enrolment of patients in the study. General staff will offer suitable patients the chance to register for the procedures. A calibrated examiner (postdoctoral researcher) will inform parents about all details of the study. If the offered is accepted, parents sign the informed consent form.

2. Initial examination and interviewing of enrolled patients and their parents by a calibrated examiner (postdoctoral researcher).
3. Random allocation in six intervention groups. This will be done by a calibrated examiner (postdoctoral researcher) using six closed envelopes containing colour codes.
4. Performing interventions according to the protocol of each study group. Those interventions will be done by Intervention Staff (IS) - four trained postgraduate students and assistants (dental hygiene students).
5. Performing and documenting emergency treatment during the follow-up period. Done by trained general staff on a daily basis according to patient needs. Registration will be done using a pre-prepared form.
6. Follow-up examination. Done by calibrated examiner (postdoctoral researcher).

Deliverables of WP4

D4.1 Enrolment registration form.

D4.2 Signed informed consent forms.

D4.3 Initial patient examination forms (including parent questionnaire).

D4.4 Intervention registration forms (including Visual Analogue Scale [VAS] of patient satisfaction).

D4.5 Emergency treatment forms (including VAS of patient satisfaction).

D4.6 Follow-up examination forms (including VAS of patient acceptance and Likert scale questions of parents acceptance).

Milestones of WP4

MS4.1 Meetings about enrollment, randomization and allocation.

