 - a. Patients received treatment outside the RSU Institute of Stomatology – every case will be analysed separately; if, for any reason, the patient attended a dentist who was not trained for the study (in the Institute of Stomatology or in another dental clinic), the recordings of treatment performed will be analysed – if there is no doubt regarding the information gained and if the treatment was done according to the guidelines used in the study, the patient will be kept in the study. In case of doubt, he/she will be excluded from analysis. This increases the risk of loss of follow-up, but it is important that we are sure about the impact of the treatment performed. Evenmore, as described above, we will include more patients than required to assure the study power even after some losses of follow-up.
 - b. Blinded research team members are informed about colour codes of the treatment groups – we will consider changing the person in case the this knowledge leads to performance or detection bias. We also will include as less personal as possible and the most motivated colleagues to avoid such errors.
 - c. Patients find out which treatment group they have been assigned to– it is possible that the groups which receive SDF “feel” the treatment to be more effective because of the staining side effect. However, we are not yet sure how important this effect will be, as all of those children have tooth damage which includes some colour change of the lesions. It is also known that arrested lesions tend to become darker even without the application of any agent. We will be able to address this risk by evaluating the patient and parent satisfaction in different treatment groups.

Infrastructure

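### Risks 2b makes replacement of an unblinded team member depend on bias the plan has no means to detect, so it permits 12-month scoring by an examiner who knows the code

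*Protocol*

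**What the plan says.** The section on randomization, allocation and blinding sets the requirement for the closing visit: "one of the calibrated examiners will perform a documentation of stage and activity of carious lesions, not knowing which treatment had been applied".

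Risks item 2b covers the breach of that requirement. The event is "Blinded research team members are informed about colour codes of the treatment groups". The response is "we will consider changing the person in case the this knowledge leads to performance or detection bias". The only other measure offered is "We also will include as less personal as possible and the most motivated colleagues to avoid such errors".

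On who examines, the protocol gives two accounts:

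- In the blinding section, parents who agree are told that "they will be assigned an appointment with one of two calibrated examiners". WP3 likewise plans "Training and calibration of two examiners on detecting the stage and activity of carious lesions".
- WP4 gives allocation to one role: "This will be done by a calibrated examiner (postdoctoral researcher) using six closed envelopes containing colour codes". It gives the closing visit to the same role: "Follow-up examination. Done by calibrated examiner (postdoctoral researcher").

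**The concern.** A blinding safeguard should act when the blind is lost. This one waits for a consequence of the loss. An examiner who knows the code and scores a little generously in an active arm produces data that look like a treatment effect. Unless a blinded second reading exists for comparison, nothing in the data separates the two.

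At stake are the outcomes that depend on the examiner's judgement: change in overall caries activity (secondary outcome A), and progression and activity of each lesion (secondary outcome B). Lesion arrest is a stated secondary objective in WP4, and lesion progression also enters the tooth-level cost-effectiveness measure (secondary outcome F).

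**Working it through.** The protocol gives no figure for this point, so the check is mainly a comparison of its provisions.

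**1. Trigger.** The blinding section makes ignorance of the treatment a condition of the 12-month examination. Item 2b makes bias, not knowledge, the condition for acting. An examiner who knows the code but has not been shown to be biased fails the first provision, yet calls for no action under the second.

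**2. Strength of the response.** Even when bias is accepted, replacement is only to be considered. Item 2b does not require it in any case.

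**3. Can the trigger be observed?** The blinding section gives each child one closing examination by one examiner. The protocol describes no repeat reading at 12 months by the other examiner, no test of whether the examiner can guess the treatment, and no record of unblinding. Examiner calibration in WP3 is a training step and is not described as a check on 12-month scores. Under this plan the condition in item 2b has no means of being met.

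**4. How knowledge reaches a child's score.** Two facts are needed: what a colour means, and which colour the child has.

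- Colours denote groups, not individual children, so one disclosure concerns a whole arm.
- The examiner draws the envelope at enrolment and so presumably knows the colour of the children he or she allocated. WP4 gives allocation and follow-up to the same role.
- Intervention staff are told which product each group receives, so the information is held within the institute.

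**5. Ceilings on the number exposed.** With 70 children per group and 420 in all (sample size section):

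| Disclosed | Children at most | Share |
|---|---|---|
| One colour | 70 | 70/420 = 16.7% |
| Both colours of one agent | 140 | 140/420 = 33.3% |
| All six colours | 420 | 100% |

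Each line assumes that one examiner scores every child concerned, knows every such child's colour, and learned the meaning before any follow-up visit. Children allocated by the other examiner, lost to follow-up, or examined before the disclosure reduce the number.

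**6. Size of the shift (assumption only).** Suppose a share *a* of children in an active arm truly has active caries, and an unblinded examiner wrongly calls a fraction *m* of them inactive. The arrest rate then rises by *m* × *a*. With *m* assumed at 5% to 10% and *a* at most 1, the rise is at most 5 to 10 percentage points in the children affected. The protocol supplies neither *m* nor *a*.

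**The case against.** The strongest reply is that item 2b is an entry in a risk list and does not repeal the blinding section. An examiner who knows the code still fails the requirement there, so a careful team would replace that person anyway. This stands as far as it goes: a reader might infer that the protocol tells an unblinded examiner to continue, and no sentence says so. But item 2b is the only text written for this event, and it permits what the blinding section rules out.

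Other objections also stand in part:

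- **Primary outcomes.** A reader might infer that pain and abscess history are biased too. The protocol does not say who records them, and emergency treatment is documented separately by general staff. Any effect there is inference.
- **Whole arms unblinded at once.** The examiner must also know each child's colour. Later treatment visits are with intervention staff only, and nothing shows the colour on the follow-up form.
- **Bias unobservable.** Double examination could give some indication. The claim is only that this plan describes no such check.
- **Logging and sensitivity analysis.** These may sit in the data management plan or an analysis plan not shown. Their absence here is not the fault; the trigger is.
- **SDF staining.** Staining may reveal SDF whatever happens to the code. That limits the gain but does not remove it. Item 2c notes that arrested lesions darken without any agent. Staining is not described as separating two applications from four, and the background presents Tiefenfluorid as avoiding the black stain. For Tiefenfluorid against placebo, and for the comparison of schedules, concealment of the code remains an important protection.

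**Conclusion.** The point holds as a badly set conduct rule. Item 2b ties action to bias that the plan has no means to detect, makes the action optional, and so permits scoring that the blinding section forbids.

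The main exposure is secondary outcomes A and B, for children whose colour the unblinded examiner knows, such as those that examiner allocated. The counts of 70, 140 and 420 are ceilings, the likelihood of a disclosure is not known, and the size of any bias is unknown. The documents do not support a claim that the trial's primary comparison is compromised.

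The conclusion rests on reading the blinded team members in item 2b as including the examiners. The item does not name them, but they are the staff whose blinding the protocol requires at 12 months.

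**What to change.** Rewrite item 2b so that knowledge of the code is the trigger:

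- An examiner who learns the product behind any colour does no further 12-month examinations, and the other, still-blinded calibrated examiner takes over. This should cover all children. Barring the examiner from one colour only would leave that arm scored mainly by the other examiner, which confounds examiner with arm, and booking visits by colour could itself hint at allocation.
- Record the date and the colour disclosed. Flag the 12-month examinations already done with knowledge of the code.
- Repeat the activity and progression comparisons without the flagged examinations, as a sensitivity analysis.
- Reconcile WP4, which names only the postdoctoral researcher for follow-up, with the blinding section and WP3, which provide two calibrated examiners. The substitute must be allowed to do follow-up examinations.

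The cost is a few sentences and a log. Both examiners are already to be trained and calibrated. The downsides are less flexible scheduling after a disclosure and a change of examiner partway through follow-up. The remedy works only while the second examiner remains blinded, and it does nothing about staining.

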- 4) the level and development of the caries damage and activity (ICDAS, Nyvad criteria).

Outcome measures:

- I. Primary outcome measures:
 - A. Pain history during the observation period, assessed as Yes/No at 12 months follow-up visit.
 - B. Abscess history during the observation period, assessed as Yes/No at 12 months follow-up visit.
 - C. The number of newly extracted or otherwise surgically treated teeth during the observation period, assessed as a number of extracted teeth during the last year at 12 months follow-up visit.
- II. Secondary outcome measures:
 - A. The change in the overall activity of caries as Active/Non-active, assessed at 12 months follow-up visit.
 - B. The progression and change of activity of every lesion, assessed by ICDAS (for progression) and Nyvad (for activity) criteria, at 12 months follow-up visit.
 - C. The parent’s satisfaction with the way their children’s teeth look, assessed by questionnaire, asking: “Are you satisfied with the way your child’s teeth look?”

- and “Would you agree to repeat the treatment procedure used?”, both measurements in 5-point Likert scale, assessed at 12 months follow-up visit.
- D. The child’s satisfaction with their teeth, measured by the visual analogue scale (VAS) with 3 points - happy, not sure, sad, assessed at 12 months follow-up visit.
 - E. The child’s feelings during the treatment, measured by the modified Wong-Baker scale with 3 options - no hurt, hurts a little, hurts a lot), assessed during every appointment (depending on treatment group can be assessed at baseline, 1, 2, 3 weeks and 12 months; or at baseline, 6 and 12 months).
 - F. The direct costs of the treatment and the cost-effectiveness, calculated as EUR spent per treatment protocol; EUR per prevented major complications (in patient-level - pain, abscess, extraction) and EUR per prevented minor complications (in tooth-level - progression of caries lesion), the calculation will be made at 12 months follow-up.
 - G. The treatment method’s undesirable side effects, assessed by parents’ questionnaire at the 12 months follow-up visit.

Statistical analysis

Data will be digitized, by entering in an ad-hoc form in the Google Docs programme. Further the data will be exported cvs (comma separated values) to an archive. Missing data will be eliminated from the analyses, marking them NA.

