1. **WP1** Project management and coordination. **The objective of WP1** is the coordination of all administrative issues before and during the study. It includes the administration of the study, obtaining all permissions needed for the study, financial management, communication with a partner institution, communication with the project commission, controlling the project and assessment of project quality and progress. Tasks to be performed in WP1 are described in details in point 3.2 of this proposal.

Deliverables of WP1

D1.1 Mid-time report, financial and technical reports.

D1.2 Final project report.

2. **WP2** Development and validation of instruments. **The objective of WP2** is to create and validate questions to patients and parents, visual analogue scales (VAS) and systems to assess the stage and activity of carious lesions. The following tasks will be performed:
 1. Creation of informative letter to patients and informed consent form.
 2. Formulation of questions to detect patient factors, which could potentially affect the outcome of treatment.
 3. Creation of a questionnaire to assess children's level of satisfaction with the treatment procedure.
 4. Creation of a questionnaire to assess children's satisfaction with the appearance of their deciduous teeth.
 5. Creation of a questionnaire to assess parent satisfaction with the appearance of their child's teeth.
 6. Modification of existing systems to detect the stage of a carious lesion (ICDAS) and activity (Nyvad).

Deliverables of WP2

D2.1 Informative letter with informed consent form.

D2.2 VAS to assess patient satisfaction after treatment.

D2.3 Form to register any emergency treatment performed in the time of the study.

D2.4 Examination form to be used at the beginning of the study – includes questions about risk factors and clinical examination form.

D2.5 Examination form to be used at the follow-up visit – includes Likert scale questions about parental acceptance of the performed treatment, questions about risk factors, VAS to evaluate patient satisfaction with the treatment performed and clinical examination forms.

D2.6 Report of adaptation of ICDAS and Nyvad systems to be used in deciduous dentition with the objective of analysing the effectiveness of treatments performed according to the type of lesion.

Milestones of WP2

MS2.1 Communication with scientific consultants and experienced partners from the University of Michigan and the University of Dundee.

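### Comparing satisfaction between groups cannot address the risk that SDF families, cued by staining, perceive more benefit

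*Protocol*

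**What the plan says.** Protocol, Risks, item 2c, considers families finding out their group. It states that "it is possible that the groups which receive SDF “feel” the treatment to be more effective because of the staining side effect", adds that the importance of this is uncertain because lesions may be discoloured in any arm, and closes with the remedy: "We will be able to address this risk by evaluating the patient and parent satisfaction in different treatment groups".

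The satisfaction measures are fixed under Outcome measures, II.C and II.D. Parents answer two 5-point Likert items at 12 months: "Are you satisfied with the way your child’s teeth look" and "Would you agree to repeat the treatment procedure used". The child's item is "The child’s satisfaction with their teeth, measured by the visual analogue scale (VAS) with 3 points - happy, not sure, sad". The section on randomization, allocation and blinding describes the 12-month instruments in the same terms: "The questionnaires for the parents and children about their satisfaction with the appearance of their teeth will be applied".

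That section also lists what families are told before consent. Its item 2 says that lesions darken when arrested, that the treatments (SDF above all) can add to this, and "therefore the teeth can become unattractive".

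Pain history and abscess history, each Yes/No at the 12-month visit, are primary outcomes I.A and I.B. Separately, WP2 deliverable D2.3 is a "Form to register any emergency treatment performed in the time of the study", and D4.5 lists the completed forms among the trial's deliverables.

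**The concern.** The remedy is stated as one that works, but it does not match the risk. The risk is about belief: a family sees staining, concludes that an active product was used, and judges or reports the child's year more favourably. The remedy measures something else, mainly how the teeth look. The cue that would create the belief is also a reason to like the look of the teeth less, so belief and staining can pull satisfaction in opposite directions.

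At stake is how the parent-reported primary outcomes are read in SDF versus placebo. Pain history is the most exposed, because it rests on recall by families who may have guessed the treatment. Abscess history is less exposed, and the number of extracted teeth less again. If the satisfaction comparison is offered as the answer to this risk, readers may take from it an assurance that it cannot give, in either direction.

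**Working it through.** The plan gives no figure on this point, so there is none to reproduce. The check compares the items with the risk and then works through assumed values.

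**Step 1. Items against the risk.**

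| Item (Outcome measures) | Asks about allocation? | Reflects perceived benefit? | Can staining lower it? |
|---|---|---|---|
| Parent: look of the teeth (II.C) | No | Not directly | Yes, by the consent information itself |
| Parent: would repeat (II.C) | No | Partly, mixed with appearance, taste and discomfort | Yes |
| Child: satisfaction with teeth (II.D) | No | Not directly | Yes |

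**Step 2. What the comparison can identify.** Let D be the SDF-minus-placebo difference in mean satisfaction, B the rise due to believing the treatment worked, and S the fall due to staining. Then D = B − S. One quantity is observed and two are unknown, so D does not determine B.

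A simulation shows this. All effect sizes are assumptions. Each side has 98 children (two arms of 49), satisfaction has SD 1, tests are two-sided at 5%, the true pain rate is 30% on both sides, and there are 4,000 runs. Under-reporting is relative.

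| B (SD) | S (SD) | SDF under-reporting | Mean D | Satisfaction test significant | Reported pain, SDF − placebo | Pain test significant |
|---|---|---|---|---|---|---|
| 0.5 | 0.5 | 30% | 0.00 | 5% | −9 points | 32% |
| 0.5 | 1.0 | 30% | −0.50 | 94% | −9 points | 31% |
| 0 | 0.5 | none | −0.50 | 94% | 0 points | 5% |

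Row 1 has bias and no satisfaction difference. Rows 2 and 3 give the same satisfaction result, one with bias and one without. The simulation lets every SDF family under-report and no placebo family (0.30 × 0.30 × 1 = 9 points). It shows the mechanism and is not an estimate of size.

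**Step 3. Possible size.** With no true effect, let P be the true rate, u the relative under-reporting among families who believe the treatment worked, and b the share who believe. The reported rate is P × (1 − b × u), so the spurious difference is P × u × (b_SDF − b_placebo). P = 0.30 is borrowed from the Protocol's sample size section, where it is the overall complication frequency in untreated waiting-list children and not a pain rate. The values of b and u are assumptions.

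- b_SDF 0.6, u 0.2: SDF 0.30 × (1 − 0.12) = 26.4%
- b_SDF 0.6, u 0.3: SDF 0.30 × (1 − 0.18) = 24.6%
- b_SDF 0.9, u 0.3: SDF 0.30 × (1 − 0.27) = 21.9%

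The placebo rate is 30% if no placebo family believes. If 40% do, it is 0.30 × (1 − 0.08) = 27.6% at u 0.2 and 0.30 × (1 − 0.12) = 26.4% at u 0.3.

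| b_SDF, u | Spurious difference, placebo belief 0% | Placebo belief 40% |
|---|---|---|
| 0.6, 0.2 | 3.6 points | 1.2 points |
| 0.6, 0.3 | 5.4 points | 1.8 points |
| 0.9, 0.3 | 8.1 points | 4.5 points |

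The range is about 1 to 8 points.

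**The case against.** The strongest reply is that this is one hopeful sentence in a risk list. Risk 2c sets no threshold, does not mention pain or abscess, and fixes no analysis. Emergency treatment is already recorded as it happens, and an SAP may hold further sensitivity analyses. This largely stands as a limit on severity. It does not make satisfaction a suitable measure: the sentence says that the comparison addresses the risk, and it does not.

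Three stronger readings are tempting, and the documents do not support them.

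- A reader might infer that SDF satisfaction should be expected to come out equal or lower, and that the trial would then declare no bias. The Protocol states no such reading rule. It says only that teeth can become unattractive. It also tells families that darkening accompanies arrest, which some may welcome, and notes that arrested lesions darken without any agent. The net direction is unknown.
- A reader might infer that no item touches perceived benefit. Willingness to repeat may do so in part, and D2.5 describes questions on parental acceptance of the treatment. The forms themselves are not shown.
- A reader might infer a spurious benefit of 8 points, to be set against the planned 20-point difference. That figure assumes no belief at all in the placebo arms, although placebo children also receive a varnish and their families hear the same explanation. It also treats an overall complication rate as a pain rate, so the two differences are not the same quantity. At 40% placebo belief it falls to 4.5 points.

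**Conclusion.** The point holds in limited form. Comparing satisfaction by group cannot show whether staining-induced belief has biased the parent-reported outcomes, because the items do not measure perceived allocation, capture perceived benefit only indirectly, and can be lowered by the same staining. This conclusion needs only the Protocol's own description of the items and of staining; it does not depend on the simulation. The link from belief to reported pain is an inference, plausible for a history taken at 12 months but not stated in Risk 2c. The size of any bias is unknown: about 1 to 8 percentage points under the assumed values, and zero if belief and under-reporting are alike across arms.

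**What to change.** In Risk 2c, delete the claim that evaluating satisfaction addresses this risk. Keep satisfaction as an acceptability outcome, which is the role it already has among the secondary objectives in WP4.

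Name instead one sensitivity analysis for this risk: repeat SDF versus placebo using complications documented on the emergency-treatment form (D2.3, D4.5), and report it alongside the parent-reported histories.

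The cost is small, since the form is already planned. Three limits should be stated with it: there will be fewer events and so less precision; documented events still depend on families seeking care, which belief can also affect; and care received elsewhere may be missed.

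A question on which product the family thinks was used is optional and descriptive only. If it is added, it is better asked early as well as at 12 months, because a late guess is confounded with real efficacy. It would describe unblinding without removing the bias.
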